4.1.2.3 PRESENTATION OF RESULTS

The primary endpoint will be analyzed on the FAS population and additionally on the PP population as sensitivity analysis.

A frequency tabulation will be provided for the disease status as collected in the CRF per analysis visit. This includes the status 'CR while being off OCS therapy for at least 8 weeks'. For participants who received rescue therapy, only assessments prior to or on the start date of rescue therapy will be considered.

Frequency tabulations will be provided of the percentage of participants who are in CR while receiving efgartigimod PH20 SC or placebo and have been off OCS therapy for ≥8 weeks at week 36 (composite strategy - primary endpoint). The table will be repeated for subgroups, including treatment differences in proportions with 95% Wald CI (with continuity correction).

The proportion of participants with BP who are in CRoff at week 36 will be tested by means of a Cochran-Mantel-Haenszel (CMH) test stratified for the 2 stratification factors of disease history (newly diagnosed versus relapsing) and disease severity as per IGA-BP at screening (moderate versus severe). The common (conditional) odds ratio will be provided, along with the exact 95% CI and 2-sided p-value from the CMH association test. In addition, the Klingenberg 95% CI for the strata-adjusted difference of proportions along with its midpoint estimate will be provided. Homogeneity of the odds ratios will be tested by means of a Breslow-Day test with Tarone's adjustment.

A sensitivity analysis will be performed on this primary endpoint using exact logistic regression with fixed effect terms for randomized treatment and stratified for the 2 stratification factors of disease history and disease severity as per IGA-BP at screening. Treatment groups will be compared in terms of the (conditional) odds ratio with 95% CI. A non-linear model with fixed effect terms for randomized treatment and the 2 stratification factors will be fitted to obtain the estimated treatment difference in proportions with 95% CI.

The same CMH test as for the primary analysis will be applied for the supplementary analysis (using a treatment policy strategy).

All sensitivity and supplementary analyses for the primary endpoint will be performed both for the analysis of study Part A, study Part B and pooled study Part A and B.

A listing will be created for the disease status at each visit, presenting the result as collected in the CRF and the result when taking into account intercurrent events (composite strategy) and rescue therapy (non-responder).

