4.1.2. Conduct of Both Parts A and B

Parts A and B of the study have different sample sizes; otherwise, both parts are identical in schedule, structure, assessments, and conduct. Both parts A and B have screening periods

of up to 2 weeks (extendable to 3 weeks per investigator discretion) followed by treatment periods of 36 weeks, during which participants will receive either efgartigimod PH20 SC or placebo. Finally, all part A and part B participants who complete the end of treatment period (EoTP) visit at week 36 will be offered the option to either enroll in an open-label extension (OLE) study or complete a 7-week treatment-free follow-up period.

To enter the study, participants must have a diagnosis of BP that complies with the international guidelines for the diagnosis of BP. ^{19,20,21} The diagnosis of BP must be confirmed by all 3 of the following methods before the participant is randomized to a study arm (refer to inclusion criterion 3):

- Clinical signs of BP (presence of bullae), with or without the presence of urticarial, eczematous, or erythematous plaques, and with or without pruritus.
- Histopathological and direct immunofluorescence (DIF) examination of a cutaneous biopsy.
- Serology by indirect immunofluorescence (IIF), chemiluminescence enzyme immunoassay (CLEIA), or ELISA.

In part B, study participants will be stratified by disease history (newly diagnosed or relapsing) and disease severity (moderate BP [an Investigator Global Assessment of Bullous Pemphigoid {IGA-BP} score of 3] or severe BP [an IGA-BP score of 4]). The participants will be randomized in a 1:1 ratio to receive either efgartigimod PH20 SC or placebo as follows:

- Efgartigimod PH20 SC will be administered by SC injection on day 1 and day 8 at a dose of mg (administered as separate SC injections of 1000 mg each), followed by single weekly SC injections of 1000 mg from week 2 through week 35.
- Placebo (injection vehicle coformulated with 2000 U/mL of rHuPH20) will be administered using the same regimen described above.

All participants will also receive concurrent therapy with OCS, ie, prednisone at a starting dosage of 0.5 mg/kg/day at baseline, or an alternate OCS at an equivalent dose strength. The OCS dosage will be adjusted according to each participant's BP disease status throughout the study. BP disease status terminology definitions are listed in Section 4.1.3 and the oral prednisone dose adjustment procedure is described in Section 6.8.1.3.

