6.3. Measures to Minimize Bias: Randomization and Blinding

The site will enroll the participant and a unique participant ID will be automatically allocated through interactive response technology (IRT) at the first screening visit.

The results of all screening procedures have to be available before baseline (week 0) to determine the eligibility for entering the study. Randomization should be performed as soon as the participants meet the appropriate criteria to begin treatment.

Upon confirmation of eligibility at baseline (week 0), the participant will be randomized through IRT. Participants will be randomized in a 1:1 ratio to receive efgartigimod PH20 SC or placebo.

At randomization, part B participants will be stratified by region (China, Japan, rest of the world). Participants who comprise the "rest of the world" stratum will be further stratified by disease history (newly diagnosed or relapsing) and disease severity (severe [IGA-BP score of 4] or moderate [IGA-BP score of 3]).

Because this is a randomized, double-blinded study, access to the IMP treatment assigned will be limited. No study team members from the investigating staff, sponsor staff who are directly involved in study management, or sponsor designees (except for staff at specialized laboratories who are responsible for PK, PD, and ADA analysis) will have access to the information related to IMP treatment assigned until after database lock.

Efgartigimod PH20 SC is a colorless to yellowish solution, while placebo is a colorless solution. To ensure that participants and site staff remain blinded to IMP, both efgartigimod PH20 SC and placebo will be provided in masked glass vials; additionally, amber-colored syringes will be used for the preparation and administration of IMP (Section 6.2.1).

An independent unblinded data and safety monitoring board (DSMB), including an independent statistician, will review all unblinded safety data as specified in Section 10.1.5.

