- If CR information is missing for the primary endpoint, the participant will be considered a nonresponder. Further details on other imputation techniques for missing CR information will be provided in the SAP.
- Details on handling other missing data will also be provided in the SAP.

Final analysis model: the proportion of participants with BP who are in CR while receiving efgartigimod PH20 SC or placebo and have been off OCS therapy for ≥8 weeks at week 36 will be tested using a Cochran-Mantel-Haenszel (CMH) test stratified for the 2 stratification factors of disease history (newly diagnosed versus relapsing) and disease severity (moderate versus severe). The odds ratio will be provided, along with the 95% CI and 2-sided p-value.

Supplementary analyses: to facilitate interpretation of the estimated treatment effect in the primary analysis, supplementary analyses will be conducted on the supportive estimand where the main ICEs are handled differently (eg, by using the hypothetical or treatment policy strategy instead of composite strategy). Details will be provided in the SAP.

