9.3.3. Secondary Endpoints Analysis

9.3.3.1. Analysis of Secondary Efficacy Endpoints (Part B Only)

For part B, there are 5 proposed key secondary endpoints subject to alpha control:

- 1. Cumulative dose of OCS from baseline to week 36.
- 2. Proportion of participants who achieve an IGA-BP score of 0 while receiving efgartigimod PH20 SC or placebo and have been off OCS therapy for ≥8 weeks at week 36.
- 3. Proportion of participants who achieve CDA while receiving efgartigimed PH20 SC or placebo and remain free of relapse through week 36.
- 4. Proportion of participants who are in CR while receiving efgartigimed PH20 SC or placebo and have been receiving minimal OCS therapy for ≥8 weeks at week 36.
- 5. Changes from baseline in the 24-hour average itch score from the Itch NRS.

Details on how to deal with the main ICEs for the proposed key secondary endpoints will be provided in the SAP.

The first proposed key secondary endpoint—cumulative dose of OCS from baseline to week 36— will be analyzed in the form of a normalized cumulative OCS dose (NCOD), normalizing by weight and by number of days in study and will be denoted as NCOD.

For the NCOD endpoint, the analysis of covariance (ANCOVA) model will be used to compare both study arms. The model will include treatment and the stratification variables will be considered as factors. Other secondary efficacy endpoints will be analyzed in a similar fashion, as described below:

- Cumulative OCS dose at the time the participant exhibits CDA, CR, and CR while receiving efgartigimod PH20 SC or placebo and receiving minimal OCS therapy for >8 weeks
- CR/PR while receiving efgartigimod PH20 SC or placebo and off OCS therapy for >8 weeks
- Relapse

In addition to using the measure NCOD for analyzing the cumulative dose of OCS use over the study duration, the term "cumulative OCS use (mg)" will be used and analyzed using descriptive statistics.

The second, third, and fourth proposed key secondary endpoints will be analyzed using a CMH test as specified for the primary endpoint. Other secondary efficacy endpoints that are expressed as responder proportions will be analyzed similarly.

The fifth proposed key secondary endpoint—changes from baseline in the 24-hour average itch score from the Itch NRS—is measured over time and will be analyzed using a mixed-effect model for repeated measures, and the least squares mean difference will be estimated at the prespecified time point.

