4. EFFICACY, PHARMACOKINETIC, PHARMACODYNAMIC AND IMMUNOGENICITY ANALYSES

4.1 EFFICACY AND QUALITY OF LIFE

All efficacy endpoints will be analyzed on the FAS population. The primary endpoint and all 5 key secondary endpoints will also be analyzed on the PP population as sensitivity analysis.

Wherever the stratification factors will be used in the efficacy analyses, the actual values of these will be used and not the ones coming from the randomization. Also, for participants randomized without stratification, i.e., part A participants and Japanese or Chinese Part B participants, these factors will be derived in order to include these participants in the statistical models.

For all references to weeks, analysis visits are considered as described in section 2.2.4, unless specified otherwise. If multiple assessments fall within the same analysis window, only the assessment closest to the target date will be considered unless specified otherwise. Other assessments within this window will only be listed and not considered in the below analyses. Only the time to response endpoint (see section 4.1.4) will be derived using all possible measurements and not only the one closest to the target of the analysis visit. Only visits up to Week 36 analysis visit will be considered defining the different responses. For endpoints 'at week 36', the last non-missing analysis visit assessment from week 32 till week 36 will be used.

All endpoints/estimands defined as an event 'while receiving efgartigimod PH20 SC or placebo' should be handled as follows: treatment discontinuations not due to 'lack of efficacy' (but e.g., due to AE) are still considered as 'while receiving efgartigimod PH20 SC or placebo'.

[figure not shown]
Examples of SAS code for the statistical analysis procedures are provided in appendix 9.3.

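### Part B is randomised within region, but the alpha-controlled analyses adjust only for disease history and severity (for NCOD by implication): valid but conservative if region matters, and adding region to the NCOD and itch models costs little

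*SAP*

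**What the plan says.** **Randomisation.** Protocol 6.3 says: "At randomization, part B participants will be stratified by region (China, Japan, rest of the world". It goes on to say that only the rest-of-world "stratum will be further stratified by disease history (newly diagnosed or relapsing) and disease severity". That gives six randomisation strata: China, Japan, and four rest-of-world cells. Protocol 4.1.2 describes the same randomisation without region: "In part B, study participants will be stratified by disease history (newly diagnosed or relapsing) and disease severity".

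**Primary test.** Protocol 9.3.2 plans a CMH test "stratified for the 2 stratification factors of disease history (newly diagnosed versus relapsing) and disease severity (moderate versus severe". SAP 4.1.2.3 keeps it: "stratified for the 2 stratification factors of disease history (newly diagnosed versus relapsing) and disease severity as per IGA-BP at screening". That is four analysis strata.

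**Key secondaries (SAP 4.1.3.2).** The three responder endpoints repeat the primary CMH. The itch MMRM takes the two stratification factors as covariates. For NCOD, Protocol 9.3.3.1 says "The model will include treatment and the stratification variables will be considered as factors", and the SAP also names no factors.

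**General rule.** SAP 4.1 explains how the factors are obtained: "for participants randomized without stratification, i.e., part A participants and Japanese or Chinese Part B participants, these factors will be derived". The ANCOVA code in SAP appendix 9.3 is not readable in this copy.

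**The concern.** An analysis would normally carry the factors used to restrict the randomisation, or say why it does not. Here region is the first-level factor for every part B participant, yet as far as this copy shows it enters none of the six alpha-controlled analyses, and no reason is given.

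What is at stake is efficiency and clarity. Stratified allocation balances region between arms. If region is prognostic, a model without it reports a standard error that is too large, so the test rejects too rarely under the null and loses power. The key secondaries are tested in a fixed sequence, so a missed rejection on one also blocks those after it. A region effect on NCOD is plausible, though the documents do not show one: Protocol 10.13.2 supplies methylprednisolone in place of prednisone in China, and SAP 3.5.2 converts doses to prednisone equivalents.

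The unnamed NCOD factors add a smaller problem. Read with Protocol 6.3, stratification variables would include region. Read with SAP 4.1, they would not.

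**Working it through.** **1. The plan's own figure.** Protocol 9.5 states 120 participants and more than 90% power at two-sided 5%. Its response rates are blacked out, so I use the 20% and 50% of SAP 1.4.2.1 as an assumption. With 60 per arm and mean rate 0.35:

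- null SE = √(0.35 × 0.65 × 2/60) = 0.0871
- alternative SE = √(0.25/60 + 0.16/60) = 0.0827
- power = Φ((0.30 − 1.96 × 0.0871)/0.0827) = 94.1%

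This agrees with the stated power but does not strictly reproduce it.

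**2. NCOD ANCOVA.** Let R² be the share of the variance left after history and severity that region explains, and k = √(1 − R²). With region balanced by design, the true SE of the treatment effect is k times the SE reported by the model without region. Let D be the effect divided by that reported SE.

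- Power without region: Φ((D − 1.96)/k)
- Power with region: Φ(D/k − 1.96)
- Size without region: 2[1 − Φ(1.96/k)]

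Set D = 1.96 + 0.842 = 2.802, which gives 80% power at R² = 0. With N = 120 and 116 residual degrees of freedom this is an effect of 0.516 SD. At R² = 10%, k = 0.949. Power is then Φ(0.842/0.949) = 81.2% without region and Φ(2.802/0.949 − 1.96) = 84.0% with it.

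| Region R² | Without region | With region | Difference (points, unrounded inputs) | Simulated difference | Size without region |
|---|---|---|---|---|---|
| 0 | 80.0% | 80.0% | 0 | −0.02 to −0.2 | 5.0% |
| 2% | 80.2% | 80.8% | +0.55 | +0.4 to +0.7 | 4.8% |
| 5% | 80.6% | 82.0% | +1.37 | +1.2 to +1.5 | 4.4% |
| 10% | 81.2% | 84.0% | +2.72 | +2.7 to +3.0 | 3.9% |
| 20% | 82.7% | 88.0% | +5.28 | not run | 2.8% |

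The simulations used 20,000 trials per cell, permuted blocks of 4 within the six strata, a normal outcome, and China and Japan at 10% or 20% each. A separate check gave about −0.1, +0.5, +1.3 and +2.6 at 0, 2, 5 and 10%.

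The loss depends on where power is anchored. If the model with region has 90% power, omitting region leaves Φ(3.242 − 1.96/k) = 85.3% at R² = 20%, a loss of 4.7 points. If it has 80%, omission leaves 72.9%, a loss of 7.1.

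Simulated size without region ran from 3.7% to 5.3%. The simulation SE is √(0.05 × 0.95/20,000) = 0.15 points, so the top value is about 2 SE above 5% and is the largest of 32 cells.

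**3. CMH, four strata against six.** Rates were 20% against 50%, N = 120, in 24 cells. History and severity log odds ratios were 0.5 to 1.5. Region effects were 0 to 1.5, in opposite directions in China and Japan.

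- Worst for six strata: 97.1% falls to 96.1% (−1.0), with strong history and severity and no region effect.
- Best for six strata: 95.4% rises to 96.9% (+1.5), with a strong region effect and weak history and severity.
- Twelve cells gain and twelve do not.
- Size: 3.6% to 5.2% with four strata, 4.7% to 5.2% with six.

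A second simulation used 40,000 runs and larger Asian shares, up to 35% and 25%. Six strata gained at most 1.3 points up to a region odds ratio of 3. At odds ratios of about 6 to 9 the gain reached 2.3 points, and four-stratum size fell as low as 1.6%.

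**4. Itch MMRM.** Not simulated. The NCOD figures are only a rough guide to its week 36 contrast.

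**The case against.** The strongest reply is that the plan is consistent. Protocol 9.3.2 and SAP 4.1.2.3 agree on two factors. SAP 4.1 derives the factors for Japanese and Chinese participants, which makes sense only for history and severity, and 4.1.2.3 and 4.1.3.2 speak of two. So the NCOD factors can be inferred, and unreadable code is not missing code. This largely stands: the intended reading is probably history and severity. It explains the wording but gives no reason for leaving region out.

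Four further readings go beyond the documents.

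- A reader might fault SAP 6.1 for not listing the omission of region. That section lists departures from the protocol, and on the CMH factors there was none.
- A reader might take SAP 4.1 to deny any stratification in China and Japan. In context it can mean without those two factors, which fits Protocol 6.3.
- A reader might conclude that region is barely reported. SAP 3.1 tabulates country and site, 3.2.3 tabulates region, 4.1.6 and 4.3.3 use it for subgroups, and 2.4 repeats descriptive outputs for Japan and China. For the primary endpoint, "The table will be repeated for subgroups, including treatment differences in proportions with 95% Wald CI (with continuity correction". None of these is a comparison adjusted for the randomisation regions: the subgroups merge Japan and China into Asia, and the Japanese set is defined by birth, residence, nationality and ancestry.
- A reader might want the primary test moved to six strata. The simulations do not support that as a clear gain, because those strata drop the history and severity adjustment inside China and Japan.

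It is also fair to object that the fix leaves four of the six alpha-controlled tests unchanged. That is deliberate: the benefit is one-sided for a linear model and two-sided for CMH.

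**Conclusion.** The mismatch is real and is a matter of efficiency and specification. It does not threaten validity: leaving region out makes the tests conservative if region is prognostic, and a reading that type I error is inflated has no support here.

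Adding region to the NCOD model changes power by about −0.1 points at R² = 0, +0.5 at 2%, +1.3 at 5%, +2.6 at 10% and about +5 at 20%. The loss from omission is therefore small only if region explains little of the NCOD variance. For the CMH tests the direction is not settled within the main range examined.

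Regional shares, region effects, history and severity effects, block size and the normal NCOD outcome are all assumptions, because the documents give none of them. The textual mismatch is certain; the magnitudes are conditional.

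**What to change.** 1. In the part B NCOD ANCOVA and itch MMRM, keep history and severity and add the randomisation region (China, Japan, rest of world) as a factor. Name the NCOD factors in the text. Say whether endpoints that borrow these models in SAP 4.1.4 (such as BPDAI, worst itch and C-GTI) follow.
2. Keep the four-stratum CMH for the primary and the three responder key secondaries. The Klingenberg difference, exact logistic and non-linear models then stay on the same two factors. Add a CMH on the six randomisation strata as a sensitivity analysis of the primary endpoint, and state whether it uses the actual history and severity values, as SAP 4.1 requires elsewhere.
3. For consistency only: bring Protocol 4.1.2 into line with 6.3, say in SAP 4.1 that Japanese and Chinese part B participants were stratified by region but not by history or severity, and give the reason region is left out of the CMH.

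**Cost.** Two NCOD residual degrees of freedom (116 to 114) and at most about 0.2 points of NCOD power if region is not prognostic. Beyond that: two model statements, one table and some wording, all before part B is unblinded. The primary test does not change.

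**Optional and separate.** Baseline BPDAI activity as an NCOD covariate takes one more degree of freedom (113). The total worst-case cost is then about 0.5 points.

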4.1.3 Key secondary endpoints (alpha controlled)

For the analysis of study Part B, the below endpoints are considered as key secondary endpoints. They will be tested in the FAS population in hierarchical order (see section 4.1.5). Additionally, the key secondary endpoints will be analysed in the PP population as a sensitivity analysis.

SGS	Statistical Analysis Plan		
ARGX-113-2009	Final and Interim Analysis	Final 4.0 of 04NOV2024	

For the analysis of study Part A, the hierarchical testing procedure will not apply.

4.1.3.1 HANDLING OF INTERCURRENT EVENTS, RESCUE THERAPY AND MISSING DATA

1) Normalized cumulative OCS dose (NCOD, mg/kg/day) over the on IMP treatment period.

Main intercurrent events are defined as follows, and handled in a 'while on treatment' strategy:

• Intercurrent medications (see section 3.4.2): stop calculating cumulative dose after ICE. In case 'immunosuppressants for at least 4 weeks in total' is the ICE, use end of the 4 weeks IC medication as stop for cumulative dose calculation. In case 'tetracyclines for at least 2 weeks in total' is the ICE, use end of the 2 weeks IC medication as stop for cumulative dose calculation. In case 'IV or IM corticosteroids' is the ICE, use the first day of this IC medication as stop for cumulative dose calculation. In case 'very potent TCS for 7 consecutive days or 14 days in total' is the ICE, use the end of the 7 or 14 days IC medication as stop for cumulative dose calculation.

Details on the derivation of intercurrent events are provided in appendix 9.1.

A supplementary analysis for this secondary endpoint will use the 'treatment policy strategy' where the occurrence of the intercurrent event is considered irrelevant: NCOD is calculated regardless of whether or not the intercurrent event occurs.

Rescue therapies will not be considered for the NCOD endpoint since rescue therapies are only permitted after discontinuation of IMP treatment and NCOD calculation is restricted to the on IMP treatment period.

- 2) The proportion of participants that have achieved IGA-BP score of 0 while receiving efgartigimod PH20 SC or placebo and have been off OCS therapy for ≥8 weeks at week 36: the same approach for handling the main ICEs (composite strategy), for the handling of rescue therapies and for handling missing data, as suggested for the primary analysis, will be applied.
- 3) The proportion of participants that have achieved control of disease activity (CDA) while receiving efgartigimod PH20 SC or placebo and remain free of relapse through week 36: the same approach for handling the main ICEs (composite strategy), for the handling of rescue therapies and for handling missing data, as suggested for the primary analysis, will be applied.
- 4) The proportion of participants that have achieved CR while receiving efgartigimod PH20 SC or placebo and while receiving minimal OCS therapy for ≥8 weeks (CRmin) at week 36:

A participant is considered as CRmin at week 36 when the reported disease status at week 36 is 'CR while receiving minimal OCS therapy for at least 8 weeks' or 'CR while being off OCS therapy for at least 8 weeks', or else when the reported disease status at week 36 belongs to a sequence of episodes with disease statuses 'CR while receiving minimal OCS therapy for less than 8 weeks *or* for at least 8 weeks' and' CR while being off OCS therapy for less than 8 weeks *or* for at least 8 weeks', having

SGS	Statistical Analysis Plan		
ARGX-113-2009	Final and Interim Analysis	Final 4.0 of 04NOV2024	

started at least 56 days earlier (and for which within these 56 days the disease status provides evidence that the participant remained in CR and the minimal OCS therapy was maintained).

The same approach for handling the main ICEs (composite strategy), for handling rescue therapies and for handling missing data, as suggested for the primary analysis, will be applied.

5) The Itch NRS is measured over time and changes from baseline in the 24-hour average itch score will be analysed. A 'treatment policy' approach will be applied by ignoring the main ICEs. For participants who received rescue therapy, only assessments prior to or on the start date of rescue therapy will be included in the analysis.

